**Plan and Pledge, HIV Self-testing in South Africa**

**NCT03898557**

**IRB Protocol #833047**

**Version 2, May 3 2019**

## **1. BACKGROUND AND STUDY RATIONALE**

Reaching the “90-90-90” targets and ending the AIDS epidemic are bold targets that motivate current efforts in HIV prevention and treatment globally. Driven by large investments of resources, these efforts have included a rapid scale-up of HIV services, including HIV testing, medical male circumcision, and antiretroviral therapy (ART). However, behavioral factors have been important barriers to maximizing the effectiveness of resources devoted to HIV/AIDS. This is particularly evident in the low uptake of HIV services among young men in eastern and southern Africa, with limited uptake of testing and linkage to HIV care in this population contributing to HIV incidence that remains above elimination targets. Insights from behavioral economics and related disciplines have highlighted various barriers to health-seeking behavior generally and also pointed to an array of low-cost interventions that have the potential to increase uptake of HIV services and promote behavior change more generally.

In collaboration with Wits Reproductive Health and HIV Institute (WRHI), University of the Witwatersrand, this pilot will incorporate behavioral insights to increase uptake of HIV self-testing in South Africa. The pilot will be part of WRHI’s STAR program (HIV Self-Testing Africa) at the fixed-distribution sites. A copy of the approved protocol for the STAR program is included in this submission.

Further background on the HIV epidemic in South Africa and HIV self-testing can be found in the attached protocol for the STAR initiative. Background for this specific pilot includes the following:

Commitment devices and planning prompts are effective strategies for individuals to translate their behavioral intentions into actions, particularly when barriers to the desired behavior include procrastination, prospective memory failures, and hassle factors [1-5]. Planning prompts may also be effective in overcoming ambiguity aversion and information avoidance, and can leverage people’s intrinsic desire to maintain a consistent self-image and also do what they believe to be the descriptive and injunctive norm [6-7].

In the context of the STAR program that is distributing HIV self-tests in South Africa, one of the desired outcomes is that individuals who obtain a self-test kit at distribution sites go on to take the test either immediately on site or in the near future at their home. A second desired outcome is that after using the self-test kit, individuals who use self-tests will report their results to a WhatsApp number that has been established for this purpose. A third desired outcome is that individuals who obtain a reactive test result will seek a confirmatory test at local clinics that provide HIV testing and counseling services. Those with a confirmed HIV-positive test result can be encouraged to seek HIV care, which includes treatment with antiretroviral therapy (ART). This pilot project will test whether commitment and planning prompts administered at the time of self-tests distribution are effective in promoting the desired behaviors.

### **1.1 Abbreviations**

- STAR program: HIV Self-Testing Africa
- WRHI: Wits Reproductive Health and HIV Institute, University of the Witwatersrand

- HIVST: HIV self-testing
- UPenn: University of Pennsylvania

## 2. STUDY OBJECTIVES

### 2.1 Primary Objective

Determine the effectiveness of commitment and planning prompts on the likelihood that self-test recipients will report the use the HIV self-test kit on a dedicated WhatsApp number

### 2.2 Secondary Objectives

Determine the effectiveness of commitment and planning prompts on the likelihood that self-test recipients will 1) consent to phone/SMS follow-up, 2) Are successfully reached for follow-up by phone about 7 days after receiving the HIV self-test, 3) Report self-test result on the dedicated WhatsApp number and are HIV positive, 4) test on-site 5) Seek confirmatory testing

## 3. STUDY DESIGN

### 3.1 General Design

This study will use a cluster randomized trial design to test the effectiveness of interventions designed to increase usage of self-test and reporting of results by HIV self-tests recipients. The intervention will build on the current WhatsApp reporting instructions distributed during self-test distribution by the STAR program. A copy of these instructions are included in this submission. The two arms in the study will be: 1) **Usual Care, “Promote”**: A card with information to report results via WhatsApp, similar to the existing card used in the STAR program. with a dedicated USUAL CARE WhatsApp number (different from the existing campaign numbers). 2) **Plan and Pledge**: The Usual Care card + a brief template to “make a plan” and “make a pledge” for test completion and results reporting, to take the test. The card will include a dedicated Plan and Pledge WhatsApp number.

Potential self-tester recipients will be shown the card, including Plan and Pledge statements if assigned to this condition, and will be encouraged by STAR field staff to use the card in their own time to make a plan and sign the pledge as part of receiving the test kit and instructions for how to complete the cards (see draft scripts below). Importantly, testers will be able to keep the card for themselves. There is no expectation to share the plan and pledge signature with the STAR field staff who distribute self-tests. Field staff will clarify for self-tests recipients that the Plan and Pledge process and card do not change the confidentiality of testing in any way.

Examples of script used for each arm:

**Usual care, “Promote”**: On this card you’ll see this WhatsApp number. After you do your screening test, you can report the test results to this number – it’s very easy, and it’s completely confidential. It’s important to report your results – positive or negative – for three reasons: 1. So we know you used the test and it went ok. 2. So we can help you understand the results. 3. If you need our support to help you get care and services you need. If you don’t have a camera on your phone, you can just text the results – see the instructions here. What questions do you have about reporting results?

**Plan and Pledge:** *Same as usual care, with the addition of:* On this part of the card, you have a place where you can make a plan to do the test – like when you'll do it, where, and if anyone will be with you when you do the test. This plan is just for you, we don't need to see it, but it's a good way to help you do the test now that you've picked it up. And then on this part of the card, you have a place where you can make a pledge or commitment to yourself to do the test and report results when you're done to the WhatsApp number. This pledge is just for you to help you carry out your plan to do the test and report results.

### **3.2 Randomization**

We will use cluster randomization with team-day pair serving as the unit of randomization (i.e. two pairs of STAR field staff will be randomized by arm and by day. Clusters of individuals will receive self-tests at a distribution site from a pair of STAR field staff on an individual day). Computer-generated randomization will be used to assign team-day pair clusters to the 2 study arms. Sites will be the STAR community fixed-point distribution sites in Tshwane District, South Africa.

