## **5. STATISTICAL PLAN**

### **5.1 Sample Size and Power Determination**

To detect a difference in the primary outcome of 5% percentage points (from 2.5% reporting to 7.5% reporting) with 80% power and at alpha = .05, with rho=.01 and cluster size per day = 30 per arm, we plan to recruit 660 participants per arm with a total of 1,320 participants.

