## **5.2 Statistical Methods**

We will compare primary and secondary outcomes in the Plan and Pledge arm to the Usual Care, “Promote” arm using 2-tailed chi-squared tests as well as logistic regression analyses. Analyses will adjust for correlation of outcomes within clusters. We hypothesize that a higher proportion of participants in the Plan and Pledge arm will report their self-test results than in the Usual Care arm, “Promote”.

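### Team-days are randomised with no stated balance by staff pair and no pair term in the model, so a stable difference between pairs would add avoidable error to the arm comparison

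*Combined protocol and SAP*

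**What the plan says.** Section 3.2 (Randomization) makes the team-day the cluster: the people who receive kits from one pair of field staff at a distribution site on one day. It says that "two pairs of STAR field staff will be randomized by arm and by day", and that "Computer-generated randomization will be used to assign team-day pair clusters to the 2 study arms". It mentions no stratification, blocking, matching or crossover by pair or by site. It refers to sites in the plural but gives neither their number nor how pairs rotate through them.

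Section 5.1 (Sample Size and Power Determination) plans 660 recipients per arm, with rho = .01 and "cluster size per day = 30 per arm".

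Section 5.2 (Statistical Methods) compares the arms "using 2-tailed chi-squared tests as well as logistic regression analyses" and adds that "Analyses will adjust for correlation of outcomes within clusters". It names no model term for pair or site.

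Section 3.3 (Study Measures) lists arm, on-site or off-site testing, and consent to a follow-up call as tracked on the intake form. Pair and site are not in that list, although the form itself is an attachment that is not shown. The analysts receive de-identified aggregate data.

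**The concern.** The contrast in section 3.1 is a card plus what staff say about it. In both arms staff explain how to report by WhatsApp and why it matters, and a WhatsApp report is the primary outcome. How clearly and persuasively a pair does this could move the reporting rate in either arm.

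If one pair is consistently better at it, two things follow. A draw that gives that pair more Plan and Pledge days shifts the estimate by part of the difference between pairs, and the planned model has no term to correct it. Even without such a draw, the difference between pairs stays in the error term. Adjusting for team-day correlation does not remove it, because that adjustment treats all the days of one pair as unrelated clusters. Balancing the list and adding one term would remove this component.

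**Working it through.** **The plan's own figure.** Section 5.1 gives 2.5% against 7.5%, 80% power, two-sided alpha .05, rho = .01 and clusters of 30.
- Design effect: 1 + 29 × 0.01 = 1.29.
- The standard two-proportion formula gives 298 per arm, and 298 × 1.29 = 385 per arm (434 from the continuity-corrected formula). The stated 660 is not reproduced.
- That mismatch is a separate matter. Here it means only that 660 per arm has about 96% power on the stated inputs.

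**Team-days.** 660 / 30 = 22 per arm, 44 in all. With two pairs working equally often, that is 22 per pair.

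**Chance of an uneven split.** Let X be the number of one pair's team-days in the Plan and Pledge arm. A 14:8 or worse split means X ≥ 14 or X ≤ 8.
- One pair in each arm every day, decided by coin flip: X ~ Binomial(22, 0.5), chance 28.6%.
- Complete randomisation of 44 team-days, 22 per arm: X is hypergeometric (44, 22, 22), chance 13.1%.

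**Shift from a 14:8 split.** Shift = (14 − 8)/22 × D = 0.273 × D, where D is the difference between pairs in reporting rate. The documents give no D, so the values below are assumptions.
- D = 2 points: 0.55 points.
- D = 4 points: 1.09 points.
- For scale, D corresponds to a pair-level correlation of (D²/4)/(0.05 × 0.95): .0021 at 2 points and .0084 at 4 points. The 4-point case would take up most of the planned rho of .01 if rho were meant to include pairs.

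**Effect on the standard error.** With no difference between pairs, SE = √[(0.025 × 0.975 + 0.075 × 0.925) × 1.29 / 660] = 1.35 points. The SD of the difference between arms in one pair's share of days is 0.152 under complete randomisation and 0.213 under the day-wise split. The total SE is √(1.35² + (SD × D)²).

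| D | Layout | SE (points) | Variance increase |
|---|---|---|---|
| 2 | complete | 1.39 | 5% |
| 2 | day-wise | 1.42 | 10% |
| 4 | complete | 1.49 | 20% |
| 4 | day-wise | 1.60 | 40% |

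**Type I error and power.** These come from simulating 44 beta-binomial clusters of 30 with rho = .01 and applying a cluster-level t-test, with and without a pair term.
- Complete randomisation, pair ignored: type I error stays near 5%.
- Day-wise split, pair ignored: 5.3% to 6.2% at D = 2 and 6.6% to 8.4% at D = 4. With the pair term it returns to about 5%.
- List balanced by pair but pair left out of the model: the test becomes conservative (4.0% at D = 2 and 1.8% at D = 4, with a 2.5% rate in both arms). With the term it is about 5%.
- Power without the term: about 95% at D = 2 under either layout. At D = 4 it is 92% (complete) or 90% (day-wise); the normal approximation gives 88% for the last case. With the term it is about 95% to 96% throughout.

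**The case against.** The strongest reply is that nothing here undermines the trial. If team-days are independently randomised, a cluster-adjusted test already allows for chance imbalance between pairs. The scripts and printed card limit how far pairs can differ, and the documents hold no evidence of a pair effect of any size. At a 2-point difference the loss is slight. This stands, and it limits the point to precision and chance imbalance. It does not cover the day-wise layout, which the wording of 3.2 together with "cluster size per day = 30 per arm" suggests. There, one pair's arm fixes the other's, and a test that treats team-days as independent understates the error.

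A second reply is that the plan is silent rather than wrong. Computer-generated assignment does not exclude blocking, and two pairs could mean two on duty each day from a larger rota. That also stands. With a larger rota the stable two-operator difference weakens, but the same remedy applies with more pair levels.

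A reader might go further and infer that site differences also distort the comparison. The documents do not settle this. If both pairs share a site on a given day, site is balanced by design; if not, site could add error of unknown size. Requiring site fixed effects is also debatable. The planned rates imply only 660 × 0.025 + 660 × 0.075 = 66 reports, spread over an unstated number of sites.

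**Conclusion.** The point holds as a modest, avoidable weakness of design and analysis. No balance by pair and no pair term are stated, and adjustment for team-day correlation does not supply either. The cost is extra variance of 5% to 10% at a 2-point difference between pairs and 20% to 40% at 4 points. An unlucky 14:8 split shifts the estimate by about 0.5 or 1.1 points. Type I error is slightly raised only if the pairs are divided between arms each day. All of this rests on an assumed difference between pairs, on two pairs working throughout, and on 30 recipients per team-day.

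Three stronger readings are not supported:
- **Systematic bias.** Randomisation favours neither arm; the risk is of an unlucky draw.
- **An underpowered trial.** Power at 660 per arm stays at about 90% or more in these settings.
- **A shift of about a quarter of the target effect.** This needs all of rho = .01 to be a fixed difference between pairs (2 × √(.01 × .05 × .95) = 4.4 points around a mean of 5%) and a 14:8 split as well: 0.273 × 4.4 = 1.2 points, or 24% of 5.

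**What to change.** **Section 3.2.** State how many pairs take part and whether one pair works in each arm every day. Randomise team-days in blocks so that each pair serves equally often in each arm, with varied block sizes to limit predictability. Fix each pair's site for the day before its arm is revealed. Where feasible, run both arms at the same site on a given day.

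**Section 5.2.** Include staff pair as a fixed effect in the cluster-adjusted primary logistic regression. The term is needed even when the list is balanced by pair, so that the standard error reflects the balance. If the arms cannot share a site each day, adjust for site in a sensitivity analysis rather than in the primary model.

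**Section 3.3.** Record pair, site and date for each kit, and carry these fields into the data set sent to the analysts.

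**Cost.** A restricted list in place of an unrestricted one, one extra model term and three recorded fields; no extra participants or staff. The downside is a slightly more predictable list. The change has to be made before randomisation starts, because balance cannot be restored later and unrecorded fields cannot be adjusted for.

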### **3.3 Study Measures**

The study will be implemented by WRHI. UPenn will only partake in the design and the analysis of de-identified aggregate data. As such, all study procedures will be conducted by the WRHI team and reviewed by the University of Witwatersrand IRB. WHRI will share any modifications submitted to Witwatersrand IRB with the UPenn team, and the UPenn team will share these documents with UPenn IRB according to the specific requirements and procedures of the UPenn IRB.

During distribution of the self-tests, an intake form will be completed (a copy of this form can be found in the attached STAR SOP). This form will track the self-test recipient's arm assignment, on-site or off-site testing, and consent for follow-up phone call.

If a self-test recipient messages the WhatsApp number or receive a follow-up call, they will be asked the following series of questions (questions are sequential and continuation of questions is dependent on response to previous question): Did they use self-test? What is their test result? (if they are willing to share), Would like a confirmatory test? Did they attended confirmatory testing? What was the confirmatory test result? Would they want to be linked to care? What date were they linked to care? ART initiation? Date of ART initiation? Linked to VMMC? Date of VMMC?

As outlined in the attached STAR WhatsApp card, all text messages are confidential and de-identified. Data tracking record keeping is also de-identified with only the HIV self-test kit bar code recorded.

Please see section 5 Statistical Plan for outcomes and analysis.

## **STUDY POPULATION AND DURATION OF PARTICIPATION**

### **3.4 Duration of Study Participation**

The intervention will be implemented at the time of HIV self-test distribution and there is no follow-up period. Participants are instructed to use the HIV self-test at home and complete the Plan and Pledge form whenever they choose. If the participants opts to test on-site, they can complete the Plan and Pledge on-site as well. Participants are asked during distribution if they would like to receive a follow-up call, as part of standard procedures with the STAR program. Follow-up calls will be made by the WRHI team about 5 days after distribution. Follow-up calls may include, if the individual used the HIV self-test, if they are willing to share their test result, and questions about the Plan and Pledge intervention, such as if the individual completed the Pledge and Plan cards.

### **3.5 Total Number of Subjects and Sites**

Our target enrollment will be approximately 1,320 self-test recipients, with about 660 recipients per arm. Project site will be the Tshwane district, South Africa.

### **3.6 Inclusion and Exclusion Criteria**

Please reference the attached STAR protocol for inclusion and exclusion criteria. This study will be implemented by WHRI as part of the STAR program and will follow the same inclusion and exclusion criteria.

Inclusion: Must be 19 years or older

Exclusion: Any potential testers that are visibly intoxicated will be turned away, as alcohol effects the test results.

### **3.7 Subject Recruitment**

The WHRI field team will set-up a distribution tent in study site areas. Individuals walking or driving past can decide to stop by the tent to learn more about the HIV self-test and to collect for personal use. Individuals in the general area of the distribution site can self-select or volunteer to collect a HIV self-test.

### **3.8 Vulnerable Populations**

This study will not recruit vulnerable populations such as children or prisoners. The STAR program follows the South Africa National Department of Health guidelines for HIVST. According to these guidelines, pregnant women are not excluded from collecting an HIV self-test.

Collection of HIV self-tests, testing, and reporting of test results to study WhatsApp number are all optional. Participants can opt to not complete any of the testing or follow-up steps at any time. This also applies to the Pledge and/or Plan cards.

## **4. STUDY PROCEDURES**

Please reference the STAR protocol and SOP for study procedures. The UPenn study team will be part of study design and analysis of de-identified aggregate data but will not play any role in study implementation. All aspects of implementation will be managed by WRHI and the University of Witwatersrand IRB.

## **5. STATISTICAL PLAN**

### **5.1 Sample Size and Power Determination**

To detect a difference in the primary outcome of 5% percentage points (from 2.5% reporting to 7.5% reporting) with 80% power and at alpha = .05, with rho=.01 and cluster size per day = 30 per arm, we plan to recruit 660 participants per arm with a total of 1,320 participants.

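### Section 5.1's inputs do not lead to 660 per arm at 80% power: they need about 385 to 434 per arm, and 660 gives about 94 to 96% power

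*Combined protocol and SAP*

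**What the plan says.** Section 5.1 (Sample Size and Power Determination) puts the whole justification in one sentence. The effect is "5% percentage points (from 2.5% reporting to 7.5% reporting" and the operating characteristics and size are "80% power and at alpha = .05, with rho=.01 and cluster size per day = 30 per arm, we plan to recruit 660 participants" per arm, 1,320 in total. Section 3.5 repeats the target as "approximately 1,320 self-test recipients, with about 660 recipients per arm".

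Section 5.2 (Statistical Methods) settles the two remaining choices. The comparison uses "2-tailed chi-squared tests as well as logistic regression analyses", so alpha is two-sided, and "Analyses will adjust for correlation of outcomes within clusters", so a design effect applies. Section 3.2 makes the team-day the unit of randomisation. At 30 people per cluster, 660 per arm is 22 clusters per arm.

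**The concern.** A low-rate comparison of 2.5% with 7.5% is a threefold difference, and a rho of .01 with clusters of 30 inflates the size by less than a third. A target of 660 per arm looks too large for 80% power on those terms. If so, the only justification for the enrolment figure cannot be reproduced, and the trial's sensitivity is misdescribed. That matters when a null result is interpreted, and to anyone who reuses rho = .01 to plan a similar trial. It also leaves open whether there is a comfortable margin (if the stated power is the wrong figure) or almost none (if rho is).

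**Working it through.** **Inputs.** p1 = 0.025, p2 = 0.075, alpha = 0.05, power = 80%, rho = 0.01, cluster size m = 30, n = 660 per arm (section 5.1). Two-sided test adjusted for clustering (section 5.2). Equal allocation (sections 3.5 and 5.1).

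**Step 1: individually randomised size, pooled variance.**

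n = [1.96 × √(2 × 0.05 × 0.95) + 0.8416 × √(0.025 × 0.975 + 0.075 × 0.925)]² / 0.05²
= [0.6041 + 0.2577]² / 0.0025 = 297.1, rounded up to 298 per arm.

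With continuity correction: (n/4) × [1 + √(1 + 4/(n × 0.05))]² = 335.9, rounded up to 336.

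**Step 2: design effect.** 1 + (30 − 1) × 0.01 = 1.29.

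**Step 3: size for 80% power.**

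| | Individual n | × 1.29 | Clusters of 30 | People per arm in whole clusters |
|---|---|---|---|---|
| No correction | 298 | 385 | 13 | 390 |
| Continuity correction | 336 | 434 | 15 | 450 |
| Protocol | – | 660 | 22 | 660 |

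The plan's 660 is not reproduced. The excess is 660 − 434 = 226 to 660 − 385 = 275 per arm. In whole clusters it is 210 to 270 per arm, or 420 to 540 in total.

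**Step 4: power at 660.** Effective size = 660 / 1.29 = 511.6 per arm.

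z = [0.05 × √511.6 − 0.6041] / 0.3062 = (1.1310 − 0.6041) / 0.3062 = 1.72, so power = 95.7%.

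A t reference with 2 × 22 − 2 = 42 df gives 95.0%, and the continuity-corrected version gives 94.3%. In a beta-binomial simulation (40,000 trials, rho = .01, clusters of 30, cluster-level t test), 22 clusters per arm gave power 0.960 and 13 clusters per arm gave 0.802. Type I error was 0.047.

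**Step 5: difference detectable at 660 with 80% power.** 2.5% against 6.0% (normal), 6.1% (t) or 6.3% (continuity-corrected), that is 3.5, 3.6 or 3.8 points.

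**Step 6: can another reading give 660?**

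- *Cluster of 60 (both arms on one day).* The design effect is 1 + 59 × 0.01 = 1.59. The need is 473 per arm (535 corrected), and power at 660 is 91.2% (88.4% corrected).
- *One-sided test.* The need falls to 302 per arm (353 corrected).
- *Different power.* A 95% target gives 490.8 × 1.29 = 633, which rounds up to 22 clusters = 660.
- *Different rho.* Other inputs kept, without continuity correction:

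| rho | Design effect | Power at 660 |
|---|---|---|
| 0.01 | 1.29 | 95.7% |
| 0.02 | 1.58 | 91.4% |
| 0.03 | 1.87 | 86.3% |
| 0.04 | 2.16 | 81.1% |
| 0.05 | 2.45 | 76.0% |

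The first two readings keep 80% power and rho = .01 and do not reach 660. The last two do (rho at about 0.04), but each replaces a printed figure, and nothing in the documents supports one over the other.

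**The case against.** The best defence is that 80% is a floor. Section 5.1 says how many people the team plans to recruit, section 3.5 calls the target approximate, and 660 is a whole number of clusters. On that reading every printed figure can be true at once, and the fault is only an unexplained surplus. This is strained: the sentence presents 660 as the size for 80% power, and a surplus of 210 to 270 people per arm in whole clusters goes unmentioned.

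Second, something may have been left out and no printed figure may be wrong. For instance, splitting alpha over seven outcomes (the primary and the six in section 5.2.2) with continuity correction and the design effect of 1.29 gives 660.1. But that is solved backwards, section 5.1 prints alpha as .05, and no section mentions a split. An allowance for loss is also unlikely: by section 5.2.1 the denominator is all kit recipients, so a person who never reports counts as a non-event and is not lost. What stands is that 660 has several possible origins, so none should be assumed.

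Third, the reassuring power depends on rho = .01 and equal clusters. Recruitment is walk-up (section 3.7), so cluster sizes will vary. Assumed coefficients of variation of 0.5 to 1.0 lower power to 94.7% and 91.2%, which does not close the gap. A higher rho would close it, as the table shows. This stands, and is why any restated power must be conditional.

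Finally, this is a pilot described as minimal risk, and the fix does not touch its conduct. That limits the consequence but does not remove the inconsistency.

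**Conclusion.** The concern holds. On the printed inputs, 80% power needs about 385 per arm (434 with continuity correction), against 660 planned, and 660 gives about 94 to 96%. The planned size is about 70% above the requirement, or about 50% with continuity correction, so rounding is not the explanation. These figures assume two-sided alpha of .05, rho = .01, equal clusters of 30 and 1:1 allocation.

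This is an error in how the design is reported. If the printed effect, rho and cluster size are right, the trial has more power than it claims. Which item is misreported (the power, rho, the effect size or an unstated inflation) cannot be settled from the documents. It should be corrected, because section 5.1 is the only basis given for enrolment.

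**What to change.** Keep 1,320. Retrieve the original sample size calculation and correct the sentence in section 5.1 to match it:

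- If the printed rho, cluster size and effect are what was used, restate the power as about 95% for 2.5% against 7.5%, or say that 660 per arm gives 80% power for a difference of about 3.5 points.
- Otherwise, state the rho, effect, alpha or inflation that was actually used, with its reason. Take it from the original calculation and do not solve backwards from 660.

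In either case, name the formula and whether a continuity correction was applied, give the number of clusters per arm, and add a line on how power changes with rho. The cost is a check of the original calculation and a short rewording. Enrolment, randomisation and analysis do not change.
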